In Scenario 2 (high-toxicity scenario), more than 50% of simulated trials declared a dose as MTD with assumed true toxicity probability in the target interval. 35.2% of simulated trials declared 200 / 240 as MTD which has a true toxicity probability of 0.379 which is close to boundary between target dose interval and overdose interval. The high-toxicity scenario has the biggest number of stopped trials (6.5%). This is expected for such a scenario.

In Scenario 3 (low-toxicity scenario) the MTD was more often chosen as a dose combination with true toxicity probability in under-dose interval than in the target dose interval. In the majority of simulated trials (70.4%) the MTD was chosen as 200 / 240, which has an assumed true toxicity probability of 0.137 which is close to the boundary of the target dose interval.

[figure not shown]
Scenario 4 (non-logistic scenario) illustrates that even if the model assumption of a logistic dose-toxicity relationship is not fulfilled, the model still selects doses with true toxicity probability in the target interval as MTD in almost 65% of simulated trials. This illustrates that the model is not sensitive to model misspecification.

[figure not shown]
The mean patient numbers range from 11.5 patients (Scenario 2) to 13.8 patients (Scenario 3) and the maximum number of patients was 30. Therefore, the patient numbers are as expected and increase when moving away from the high-toxicity scenario.

[figure not shown]
By reviewing the metrics presented in [Table 10.5: 13](#), it can be seen that the model is not sensitive to different scenarios of truth. In general, this model is conservative due to the overdose control criteria. In all scenarios, the probabilities of recommending a dose combination with true $P(DLT) \geq 33\%$ as MTD are much smaller than probabilities of recommending a dose combination with true $P(DLT)$ between 16% and 33% as MTD.

[figure not shown]
On-study recommendations based on the model are consistent with the clinical decision making process, and should be considered in conjunction with other available clinical information by the BI clinical trial team and trial investigators in deciding the dose levels to be tested in order to determine the MTD estimate.

R version 3.5.1 and JAGS version 4.3.0 were used for data scenarios and simulations for Part B.

[figure not shown]
[figure not shown]
[figure not shown]

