10.5 STATISTICAL APPENDIX

Part A:

A BLRM with overdose control will be used to guide dose escalation in this part of the trial. The BLRM is introduced in Section 7, which also specifies the prior for the model. After patients in each cohort have completed at least one cycle of treatment, the prior distribution will be updated through Gibbs sampling procedures with the accumulated DLT data from the MTD evaluation period. Posterior probabilities for the rate of DLTs will be summarised from BLRM. Selection of the next dose will be based on these probabilities as well as on other safety and laboratory data.

The purpose of this statistical appendix is to present performance metrics (operating characteristics) that illustrate the precision of the design in estimating the MTD under various dose-toxicity relationships through computer simulation. These results are summarised in [Table 10.5: 3](#). In addition, recommendations of the next dose level by the BLRM with overdose control principle are also provided under various hypothetical outcome scenarios in early cohorts to show how it facilitates on-trial dose-escalation decisions (see [Table 10.5: 1](#)). For simplicity reasons, a cohort size of 3 patients who are all evaluable starting at 25 mg is assumed for calculation of the operating characteristics.

Hypothetical data scenarios

Hypothetical data scenarios are shown in [Table 10.5: 1](#). These scenarios reflect potential on-trial data constellations and related escalation as allowed by the model and the 100% escalation limit. It is assumed that each cohort has exactly three patients who are all evaluable. For each scenario, the probability of overdose for the current dose, as well as the next potential dose and related probabilities of under-dosing, target dose and over-dosing are shown.

For example, Scenario 1 represents the case where 1 patient has been treated at the starting dose of 5 mg and did not experience a DLT. Then, the BLRM would recommend escalating to 200 mg as the next dose. Since escalation is only allowed up to 15 mg per protocol, the next dose to be tested in the trial would be 15 mg.

Similarly, Scenario 4 represents the case where 1 patient has been treated at 5 mg and 1 at 15 mg, none of them with a DLT. In this case, the model recommends escalating to 200 mg. As this exceeds the per protocol margin, the next dose to be tested would be 25 mg.

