Scenario 3 shows the case that already the starting dose level is quite toxic, with 2 out of 3 treated patients experiencing DLTs. The overdose control implemented in the model then does not allow going to any of the pre-specified doses.

Finally, Scenario 14 and 15 illustrate a case where escalation has proceeded up to the highest dose of 400 mg. Scenario 15 represents a scenario where the MTD could be declared at 400 mg.

Table 10.5: 1 Hypothetical data scenarios

Scenario	Dose (mg)	# Patients	# DLT	Current Dose: P(OD)	Next recommended dose	Next recommended dose:		
						P(UD)	P(TD)	P(OD)
1	5	1	0	0.012	200* [15]	0.701	0.143	0.156
2	5	3	1	0.161	5	0.592	0.246	0.161
3	5	3	2	0.607	NA	NA	NA	NA
4	5	1	0	0.012	200* [25]	0.724	0.137	0.140
	15	1	0					
5	5	1	0	0.131	25	0.540	0.273	0.186
	15	3	1					
6	5	1	0	0.003	200* [50]	0.769	0.127	0.104
	15	1	0					
	25	3	0					
7	5	1	0	0.095	50	0.522	0.281	0.196
	15	1	0					
	25	3	1					
8	5	1	0	0.415	5	0.571	0.282	0.147
	15	1	0					
	25	3	2					
9	5	1	0	0.002	400*[100]	0.626	0.148	0.226
	15	1	0					
	25	3	0					
	50	3	0					
10	5	1	0	0.055	100	0.550	0.280	0.170
	15	1	0					
	25	3	0					
	50	3	1					
11	5	1	0	0.003	400*[200]	0.674	0.124	0.202
	15	1	0					
	25	3	0					
	50	3	0					
	100	3	0					

Table 10.5: 1 Hypothetical data scenarios (continued)

12	5	1	0					
	15	1	0					
	25	3	0					
	50	3	0					
	100	3	2	0.290	50	0.654	0.284	0.062
13	5	1	0					
	15	1	0					
	25	3	0					
	50	3	0					
	100	3	0					
	200	3	0	0.011	400	0.760	0.111	0.129
14	5	1	0					
	15	1	0					
	25	3	0					
	50	3	0					
	100	3	0					
	200	3	0					
	400	3	0	0.021	400	0.899	0.080	0.021
15	5	1	0					
	15	1	0					
	25	3	0					
	50	3	0					
	100	3	0					
	400	6	1	0.158	400	0.450	0.392	0.158

Operating characteristics

Operating characteristics are a way to assess the long-run behaviour of a model by illustrating the precision of the design in estimating the MTD. Under an assumed true dose-toxicity curve, metrics such as the probability of recommending a dose with true DLT rate in the target interval can be approximated via simulation. [Table 10.5: 2](#) describes 4 assumed true dose-toxicity scenarios which were used to assess the operating characteristics of the model. These scenarios reflect a wide range of possible cases as follows:

- Scenario 1: aligned with prior means
- Scenario 2: high-toxicity scenario
- Scenario 3: low-toxicity scenario
- Scenario 4: non-logistic dose-toxicity scenario

Table 10.5: 2 Assumed true dose-toxicity scenarios

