Scenario		Dose (mg)				
		25	50	100	200	400
1: Prior	P(DLT)	0.059	0.078	0.107	0.164	0.269
2: High Tox		0.259	0.278	0.307	0.364	0.469
3: Low Tox		0.009	0.028	0.057	0.114	0.219
4: Non-Logistic		0.048	0.147	0.193	0.312	0.348

For each of these scenarios, 1000 trials were simulated. Each cohort consisted of 3 patients and dose escalation complied with the following rules:

- Escalate to the dose which maximises the probability of the targeted toxicity region and satisfies the overdose criterion if it is $\leq 100\%$ increase from the current dose
- If the recommended dose satisfying the overdose criterion is $> 100\%$ increase in dose, then escalate to the highest dose level which is $\leq 100\%$ increase from the current dose.

The MTD was considered reached if at least 6 patients have been evaluated at a dose level which is the model's recommendation for the next dose cohort and for which the posterior probability of targeted toxicity was at least 50%, or if at least 18 patients have been treated in the trial, of which at least 6 at the MTD. It was then assessed how often a dose was declared as MTD with true DLT rate in the under-, targeted or over-dose range. Furthermore, the average, minimum and maximum number of patients per trial and the average number of DLTs per trial are reported. Results are shown in [Table 10.5: 3](#).

Table 10.5: 3 Simulated operating characteristics

Scenario	% of trials declaring a MTD with true DLT rate in				# Patients Mean (Min-Max)	# DLTs Mean (Min-Max)
	underdose	target dose	overdose	Stopped		
1	20.8	77.6	0.0	1.6	20.350 (3 - 42)	2.669 (1 - 8)
2	0.0	44.7	8.9	46.4	13.250 (3 - 30)	3.816 (1 - 9)
3	46.2	53.7	0.0	0.1	20.830 (6 - 39)	2.179 (1 - 6)
4	19.4	68.5	10.4	1.7	19.250 (3 - 33)	3.612 (1 - 9)

In Scenario 1 which reflects the case that the true dose-toxicity is aligned with prior means almost 78% of trials have found a MTD with true DLT rate in the target interval. 412 trials

declared 400 mg as the MTD, 364 trials declared 200 mg as the MTD. In Scenario 2 (high-toxicity scenario), almost as many trials declared a MTD with true DLT rate in the target interval, as trials that were stopped without declaring a MTD since all dose levels were too toxic. The high number of prematurely stopped trials is an expected situation for such a high toxicity scenario. Only few trials declared MTDs with true DLT rates in the overdose interval.

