Scenario 3 (low-toxicity scenario) shows that more than 50% of trials (537 of 1000) declared MTDs with true DLT rate in the target interval although only one dose level (400 mg) has assumed true DLT rate in the target interval. The majority of the rest of the trials (393 trials) declared 200 mg as the MTD. Only one trial has been stopped prematurely due to too toxic doses. Scenario 4 represents a case where the assumed true dose-toxicity curve does not follow a logistic shape. In this scenario, more than 60% of trials determined MTDs with true DLT rate in the target interval and only a few trials declared MTDs with true DLT rate in the overdose interval. The mean patient numbers range from 13.25 patients (Scenario 2) to 20.83 patients (Scenario 3) and the maximum number of patients was 39. Therefore, the patient numbers are as expected and increase when moving away from the high-toxicity scenario.

By reviewing the metrics presented in [Table 10.5: 3](#), it can be seen that the model is not sensitive to different scenarios of truth, even under misspecification results are satisfactory. In general, this model is conservative due to the overdose control criteria. In all scenarios, the probabilities of recommending a dose with true $P(DLT) \geq 33\%$ as MTD are much smaller than probabilities of recommending a dose with true $P(DLT)$ between 16% and 33% as MTD.

On-trial recommendations based on the model are consistent with the clinical decision making process, and should be considered in conjunction with other available clinical information by the BI clinical trial team and trial Investigators in deciding the dose levels to be tested in order to determine the MTD estimate. R Version 3.2.2 was used for data scenarios and simulations.

Part B:

Dose finding in Part B of the trial will be guided by a Bayesian 5-parameter logistic regression model with overdose control. For a description of the model refer to [Section 7.1.2](#).

To determine the prior distributions for θ_1 and θ_2 , a meta-analytic predictive approach will be used. Toxicity information on BI 891065 from Part A of the trial and toxicity information on BI 754091 from the Trial 1381.1 will be incorporated.

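### Table 10.5: 3 is not the output of the stated Part A rule: it shows no DLT-free trial where about 41, 118 and 7 per 1000 are expected in Scenarios 1, 3 and 4

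*Protocol*

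**What the plan says.** Protocol Section 10.5, Part A, describes the simulation behind Table 10.5: 3: "For each of these scenarios, 1000 trials were simulated. Each cohort consisted of 3 patients". On the starting point it says that "a cohort size of 3 patients who are all evaluable starting at 25 mg is assumed". Each step goes to the dose with the highest probability of targeted toxicity among those meeting the overdose criterion, with increases capped at 100%.

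The MTD is reached when at least 6 patients have been evaluated at the recommended dose and its posterior probability of targeted toxicity is at least 50%, "or if at least 18 patients have been treated in the trial, of which at least 6 at the MTD". Section 7.1.1 contains the same 18-and-6 criterion.

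Table 10.5: 3 reports DLTs per trial as mean (minimum to maximum): 2.669 (1 to 8), 3.816 (1 to 9), 2.179 (1 to 6) and 3.612 (1 to 9) for Scenarios 1 to 4. Mean patients are 20.350, 13.250, 20.830 and 19.250, with maxima of 42, 30, 39 and 33. The text below the table says that "the maximum number of patients was 39".

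Section 7.7 cites this simulation when it says that at least 20 evaluable patients are expected for the model to have reasonable operating characteristics.

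**The concern.** No simulated trial in any scenario ends without a DLT, although the written count criterion allows that and two of the scenarios have low true DLT rates. If DLT-free trials should have occurred in number, the table describes some other rule or is mis-tabulated. Section 7.7 would then rest on operating characteristics that are not those of the stated design.

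The missing outcome is also the one Part A gave. Table 7.1.2: 2 lists no DLT among 2 + 1 + 3 + 4 + 3 + 3 + 6 = 22 evaluable patients, 6 of them at 400 mg.

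**Working it through.** **1. Path of a DLT-free trial.** Table 10.5: 1 shows the recommendation after each DLT-free cohort: 50 mg after 25 mg, 100 mg after 50 mg and 200 mg after 100 mg (all limited by the cap), then 400 mg after 0/3 at 200 mg (overdose probability 0.129) and 400 mg again after 0/3 there. Those rows include one patient each at 5 and 15 mg. A grid evaluation of the model with the printed prior gives the same path without them, and still recommends 400 mg after 0/6. The trial therefore has 3 + 3 + 3 + 3 + 6 = 18 patients with 6 at 400 mg, and the count criterion stops it. Counting the 5 and 15 mg patients gives 20, which also meets the criterion.

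**2. Probability of that path.** With true rates p from Table 10.5: 2:

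P(0 DLTs) = [(1 − p25)(1 − p50)(1 − p100)(1 − p200)]³ × (1 − p400)⁶

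- Scenario 1, rates "0.059 0.078 0.107 0.164 0.269": (0.941 × 0.922 × 0.893 × 0.836)³ × 0.731⁶ = 0.2717 × 0.1526 = 0.0415
- Scenario 3, rates "0.009 0.028 0.057 0.114 0.219": (0.991 × 0.972 × 0.943 × 0.886)³ × 0.781⁶ = 0.5213 × 0.2269 = 0.1183
- Scenario 4, rates "0.048 0.147 0.193 0.312 0.348": (0.952 × 0.853 × 0.807 × 0.688)³ × 0.652⁶ = 0.0917 × 0.0768 = 0.0070
- Scenario 2, rates 0.259, 0.278, 0.307, 0.364, 0.469: 0.0131 × 0.0224 = 0.0003

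**3. Chance that none of 1000 trials is DLT-free**, (1 − q)¹⁰⁰⁰, where q is the probability from step 2:

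| Scenario | Expected DLT-free trials | Chance of none | Printed minimum |
|---|---|---|---|
| 1 | 41 | 4 × 10⁻¹⁹ | 1 |
| 2 | 0.3 | 0.75 | 1 |
| 3 | 118 | 2 × 10⁻⁵⁵ | 1 |
| 4 | 7 | 0.0009 | 1 |

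**4. The rest of the table.** The printed Scenario 1 selection rate agrees with the protocol's own text: 412 trials at 400 mg plus 364 at 200 mg is 776, or 77.6%. The grid model agrees with Table 7.1.1: 2 to about 0.01 and with Scenarios 1 to 14 of Table 10.5: 1 to about 0.015. Simulating the written rule with it, 10,000 trials per scenario, gives (re-simulated / printed):

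| Scenario | Target % | Underdose % | Overdose % | Stopped % | Mean patients | Mean DLTs |
|---|---|---|---|---|---|---|
| 1 | 74.9 / 77.6 | 21.2 / 20.8 | 0 / 0 | 3.9 / 1.6 | 19.13 / 20.35 | 2.54 / 2.669 |
| 2 | 40.8 / 44.7 | 0 / 0 | 7.7 / 8.9 | 51.5 / 46.4 | 11.82 / 13.25 | 3.40 / 3.816 |
| 3 | 57.0 / 53.7 | 42.9 / 46.2 | 0 / 0 | 0.1 / 0.1 | 19.47 / 20.83 | 1.85 / 2.179 |
| 4 | 65.8 / 68.5 | 20.3 / 19.4 | 10.4 / 10.4 | 3.5 / 1.7 | 18.44 / 19.25 | 3.41 / 3.612 |

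Simulated DLT-free trials were 4.0%, 0.03%, 11.7% and 0.7%, in line with step 2. For scale, the standard error of a 75% rate in 1000 trials is √(0.75 × 0.25 / 1000) = 1.4 points. The Scenario 1 target gap of 2.7 points is therefore about 2 standard errors. The selection gaps alone would be weak evidence; the DLT minimum is the decisive one.

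**5. Maximum trial size.** The text's 39 is the Scenario 3 value. Scenario 1 in the same table shows 42.

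**6. Scenario 15 of Table 10.5: 1.** The protocol says "Scenario 15 represents a scenario where the MTD could be declared at 400 mg". The rows as they read total 1 + 1 + 3 + 3 + 3 + 6 = 17 patients, with no 200 mg row. They give under/target/over probabilities of about 0.66/0.26/0.08 against the printed 0.450/0.392/0.158. Adding 200 mg with 1 DLT in 3 gives about 0.45/0.40/0.15, and the total becomes 20 patients with 6 at 400 mg. Adding 0 in 3 gives 0.708/0.235/0.057, which does not fit.

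**The case against.** The practical effect is small. Selection rates move by a few points, in both directions: Scenario 3 does better under the written rule than the table says. The MTD criterion is permissive and the Safety Review Committee decides. Sections 3.1 and 7.1.1 already let the committee add patients and name a recommended dose when no DLT is seen at a dose considered sufficiently efficacious, and Section 3.1 sets the Part B starting limit for the case that no MTD is identified. These simulations predate Part A, so a re-run changes no Part A dose decision. All of this stands. It limits the consequence, but it does not make the table an output of the rule printed beside it. Nor is the column unable to show zero: its Part B counterpart, Table 10.5: 13, prints a minimum of 0 in Scenario 3.

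Three stronger readings are tempting, and the documents do not support them.

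- **That the simulation required at least one DLT before stopping.** This would explain the minimum of 1, and it moves the means towards the table (Scenario 3: 20.12 patients, 2.01 DLTs). It does not reproduce the rest. In a run of 1,500 trials per scenario it gave Scenario 1 target 72.4% and stopped 4.5%, against 77.6% and 1.6%, and Scenario 2 stopped 52.6%, against 46.4%. No passage states such a condition, and a faulty summary remains equally possible.
- **That the Part A primary endpoint is reported against a different rule.** SAP Section 7.4 reports DLT counts and model posterior probabilities, with the MTD determined by the committee. It does not use Table 10.5: 3.
- **That the Scenario 15 example is wrong.** The missing 200 mg row may have been lost in converting the PDF to text. With 1 DLT in 3 restored there, the printed posterior fits and the count criterion is met.

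**Conclusion.** The concern holds as a discrepancy between the stated Part A rule and the reported simulation. In Scenarios 1, 3 and 4 the printed minimum of 1 DLT is practically impossible under that rule; Scenario 2 is compatible. This rests only on the printed DLT rates, cohorts of 3 from 25 mg, the 100% cap, the model's printed recommendations and the 18-and-6 criterion. It also holds in the variants tried without a DLT requirement, including pre-loaded DLT-free patients at 5 and 15 mg and the Section 7.1.1 wording of the criteria.

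The further gaps are about 0.8 to 1.4 in mean patients, 0.1 to 0.4 in mean DLTs and 0 to 5 points in the percentages. They depend on the re-simulation, which uses the component-1 prior mean of −2.797 from Table 7.1.1: 1 (the text has −2.787). The table's broad message of little overdose selection, with the target dose chosen in most trials in Scenarios 1, 3 and 4, survives. The rule that was simulated cannot be identified. The 39 against 42 is a plain inconsistency.

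**What to change.** Re-run the Part A simulation under the rule as written and restate Table 10.5: 3, or state the rule that was simulated and reconcile it with Section 7.1.1. Report the percentage of trials ending with zero DLTs, since that is the outcome Part A gave, and correct 39 in the text. Check Scenario 15 of Table 10.5: 1 against the source file and restore the 200 mg row if it is absent there.

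No at-least-one-DLT condition should be added to Section 7.1.1 on the strength of this point. The documents do not show that it was simulated, and adding it now would change the rule after a DLT-free Part A.

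The cost is a few minutes of simulation and a corrected appendix. Some stated rates will become slightly less favourable and others more so.

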7.7 DETERMINATION OF SAMPLE SIZE

The number of patients to be enrolled in Part A and B cannot be predicted. Only estimation is provided in this section.

Part A:

No formal statistical power calculations to determine sample size were performed for this trial part. Approximately 30 patients (including patients at the MTD) are expected to be enrolled into Part A of this trial based on the number of dose levels/cohorts that are tested. Fewer patients might be needed based on the recommendation of the SRC and the criteria specified (see Section 8.7). However, the actual number of patients will depend on the number of dose cohorts tested. Based on the simulation study to evaluate operating characteristics of the BLRM (see statistical appendix), at least 20 evaluable patients (where evaluable patients refer to patients not fulfilling the criteria for replacement [Section 3.3.4.4]) are expected to be treated in the dose escalation part for the model to have reasonable operating characteristics relating to its MTD recommendation.

Part B:

No formal statistical power calculations to determine sample size were performed for this trial part. Approximately 31-37 patients (including patients at the MTD) will be expected for this part based on the number of dose levels/cohorts that are tested. Fewer patients might be needed based on the recommendation of the SRC and the criteria specified (see Section 8.7). However, the actual number of patients will depend on the number of dose cohorts tested.

Part C NSCLC:

A justification of the cohort size for this expansion cohort is based on assumed OR rates. A futility check will be performed by the SRC when 20 evaluable patients have been treated for at least 18 weeks. If an efficacy signal, i.e. at least 2 patients with OR, is observed out of 20 evaluable patients, the total intended 40 evaluable patients will be recruited into this trial part. If this efficacy signal cannot be observed, enrolment into the trial will be stopped.

Table 7.7: 1 summarises the probabilities to stop the trial after the futility analysis assuming different true underlying OR rates.

Table 7.7: 1 Probabilities to stop the trial at the futility analysis

Assumed true OR rate (%)	Cohort size	P(< 2 patients with OR)	P(\geq 2 patients with OR)
10	20	0.39	0.61
30	20	0.01	0.99
45	20	<0.01	>0.99

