The prior distributions for both scenarios are given in [Table 10.5: 7](#) and [Table 10.5: 8](#). The corresponding prior probabilities of a DLT at different dose combinations and the corresponding probabilities of under toxicity, targeted toxicity and over toxicity are shown in [Table 10.5: 9](#) and [Table 10.5: 10](#).

Table 10.5: 7 Prior distributions for Scenario 1 (no DLTs at 400 mg in Part A)

Parameter	means, standard deviations, correlation	mixture weight
$\log(\alpha_1), \log(\beta_1)$: component 1	(-2.404, -0.364), (0.679, 0.737), -0.036	0.9
$\log(\alpha_1), \log(\beta_1)$: component 2	(-2.404, -0.364), (2, 1), 0	0.1
$\log(\alpha_2), \log(\beta_2)$: component 1	(-2.946, -0.193), (0.690, 0.884), -0.037	0.9
$\log(\alpha_2), \log(\beta_2)$: component 2	(-2.946, -0.193), (2, 1), 0	0.1
η	0, 0.56	N/A

Table 10.5: 8 Prior distributions for Scenario 2 (one DLT at 400 mg in Part A)

Parameter	means, standard deviations, correlation	mixture weight
$\log(\alpha_1), \log(\beta_1)$: component 1	(-2.040, -0.093), (0.644, 0.716), -0.095	0.9
$\log(\alpha_1), \log(\beta_1)$: component 2	(-2.040, -0.093), (2, 1), 0	0.1
$\log(\alpha_2), \log(\beta_2)$: component 1	(-2.946, -0.193), (0.690, 0.884), -0.037	0.9
$\log(\alpha_2), \log(\beta_2)$: component 2	(-2.946, -0.193), (2, 1), 0	0.1
η	0, 0.56	N/A

Table 10.5: 9 Prior probabilities of DLTs for Scenario 1 (no DLTs at 400 mg in Part A)

Dose BI 891065	Dose BI 754091	Probability of true DLT rate in			Mean	StD	Quantiles		
		[0,0.16)	[0.16,0.33)	[0.33,1]			2.5%	50%	97.5%
50 mg	240 mg	0.831	0.140	0.030	0.113	0.097	0.023	0.089	0.357
100 mg	240 mg	0.743	0.214	0.043	0.134	0.107	0.029	0.108	0.417
200 mg	240 mg	0.565	0.324	0.110	0.179	0.135	0.032	0.143	0.544
400 mg	240 mg	0.408	0.274	0.318	0.274	0.225	0.018	0.207	0.839

Table 10.5: 10 Prior probabilities of DLTs for Scenario 2 (one DLT at 400 mg in Part A)

Dose BI 891065	Dose BI 754091	Probability of true DLT rate in			Mean	StD	Quantiles		
		[0,0.16)	[0.16,0.33)	[0.33,1]			2.5%	50%	97.5%
50 mg	240 mg	0.804	0.162	0.033	0.118	0.102	0.022	0.093	0.376
100 mg	240 mg	0.684	0.263	0.053	0.147	0.113	0.030	0.119	0.451
200 mg	240 mg	0.450	0.387	0.162	0.211	0.147	0.040	0.174	0.600
400 mg	240 mg	0.297	0.268	0.435	0.342	0.248	0.026	0.282	0.905

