As can be seen from [Table 10.5: 9](#) and [Table 10.5: 10](#), the dose combinations 50 mg BI 891065 and 240 mg BI 754091, 100 mg BI 891065 and 240 mg BI 754091, and 200 mg BI 891065 and 240 mg BI 754091 have prior probabilities of over toxicity below 25% in both scenarios. They fulfill the overdose criterion and are therefore suitable starting dose combinations.

Since prior probabilities for both scenarios shown above are similar, only Scenario 2 with a starting dose combination 100 mg BI 891065 and 240 mg BI 754091 will be used to evaluate the model in terms of performance metrics and data scenarios.

Performance metrics (operating characteristics) illustrate the precision of the design in estimating the MTD under various dose-toxicity relationships through computer simulation. These results are summarized in [Table 10.5: 13](#). In addition, recommendations of the next dose combination by the BLRM with overdose control principle are also provided under various hypothetical outcome scenarios in early cohorts to show how it facilitates on-trial dose-escalation decisions (see [Table 10.5: 11](#)). For simplicity reasons, a cohort size of 3 patients who are all evaluable is assumed.

Hypothetical data scenarios

Hypothetical data scenarios are shown in [Table 10.5: 11](#). These scenarios reflect potential on-study data constellations and related escalation as allowed by the model and the 100% escalation limit. For each scenario, the probability of overdose for the current dose combination, as well as the next potential dose combination and related probabilities of under-dosing, target dose, and over-dosing are shown.

Scenario 1 represents the case that 3 patients are treated at the starting dose combination 100 / 240 and none of these patients experiences a DLT. The model recommendation then is to escalate to the combination 200 / 240. Even if one of these 3 patients experiences a DLT, the model still recommends to escalate to 200 / 240 (see Scenario 2).

Scenario 3 describes a case where de-escalation to 50 / 240 would be required. In case 2 of 3 patients at 100 / 240 experience DLTs, the overdose probability at 100 / 240 exceeds 25%, which implies that 100 / 240 cannot be tested without further data at lower dose levels.

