Scenario		Dose combination (mg/mg)			
		50 / 240	100 / 240	200 / 240	400 / 240
1: Prior	P(DLT)	0.118	0.147	0.211	0.342
2: High Tox		0.156	0.298	0.379	0.514
3: Low Tox		0.051	0.092	0.137	0.254
4: Non-Logistic		0.098	0.112	0.317	0.675

For each of these scenarios, 1000 trials were simulated. Each cohort consisted of 3 patients and dose escalation complied with the following rules:

1. Escalate to the dose combination which maximises the probability of the targeted toxicity region and satisfies the overdose criterion if it is $\leq 100\%$ increase from the current dose of BI 891065
2. If the recommended dose combination satisfying the overdose criterion is $> 100\%$ increase in dose of BI 891065, then escalate to the highest dose combination which is $\leq 100\%$ increase from the current dose of BI 891065.

The MTD was considered reached if at least 6 patients have been evaluated at a dose level which is the model's recommendation for the next dose cohort and if in total at least 12 patients have been included in the trial or if the posterior probability of targeted toxicity was at least 50% for the dose combination which is the model's recommendation for the next dose cohort and if in total at least 12 patients have been included in the trial.

It was then assessed how often a dose combination was declared as MTD with true DLT rate in the under-dose, targeted dose, or over-dose range. Furthermore, the average, minimum and maximum number of patients per trial and the average number of DLTs per trial are reported. Results are shown in [Table 10.5: 13](#).

Table 10.5: 13 Simulated operating characteristics

	% of trials declaring a MTD with true DLT rate in				# Patients	# DLTs
	Underdose	Target dose	Overdose	Stopped	Mean (Min-Max)	Mean (Min-Max)
1	19.4	70.4	9.3	0.9	12.711 (3 - 30)	2.601 (1 - 8)
2	6.9	51.1	35.5	6.5	11.538 (3 - 30)	3.648 (1 - 12)
3	76.2	23.1	0.0	0.7	13.752 (6 - 30)	2.048 (0 - 7)
4	34.5	64.9	0.2	0.4	12.414 (6 - 27)	3.007 (1 - 9)

In Scenario 1, which reflects the case that the true dose-toxicity is aligned with prior means, 70.4% of the simulated trials declared the combination 200 / 240 mg as MTD. Only 9.3% of the simulated trials declared the dose combination 400 / 240 mg as MTD, which has an assumed true toxicity probability in the overdose interval.

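### The Part B operating characteristics in Table 10.5: 13 do not come from the stopping rule that Appendix 10.5 says was simulated: the printed maxima of 27 to 30 patients are unreachable under it

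*Protocol*

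**What the plan says.** In Protocol Appendix 10.5, Part B, the model is evaluated under one prior and one start: "only Scenario 2 with a starting dose combination 100 mg BI 891065 and 240 mg BI 754091 will be used to evaluate the model". Escalation is by fixed cohorts: "Each cohort consisted of 3 patients and dose escalation complied with the following rules". There are 1000 simulated trials per scenario.

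The stopping rule has two limbs. The first reads "The MTD was considered reached if at least 6 patients have been evaluated at a dose level which is the model's recommendation" for the next cohort. The second is a posterior probability of targeted toxicity of at least 50% at the recommended combination. Each limb carries the same further condition, "if in total at least 12 patients have been included in the trial".

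Table 10.5: 13 gives mean (range) patient numbers of 12.711 (3 to 30), 11.538 (3 to 30), 13.752 (6 to 30) and 12.414 (6 to 27) for Scenarios 1 to 4. The text sums this up as "The mean patient numbers range from 11.5 patients (Scenario 2) to 13.8 patients (Scenario 3) and the maximum number of patients was 30" and describes the numbers as in line with expectation. It cites just under 65% correct selection in the non-logistic Scenario 4 as showing that the model tolerates misspecification.

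Section 7.1.2 states a different rule: posterior probability of the target interval above 0.50 with no minimum number, or at least 12 patients with at least 6 at the MTD.

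**The concern.** Once 12 patients are in, the described rule lets a trial continue only if the recommended dose has fewer than 6 patients and its probability of targeted toxicity is below 50%. With four dose combinations that leaves little room, so a maximum of 30 looks odd. If the table came from another rule, its selection, overdose and stopping percentages describe a design that the protocol does not state. These are the operating characteristics that the appendix offers in support of the Part B design.

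**Working it through.** **Inputs.** All are from the Protocol.
- Prior: Table 10.5: 8, mixture weights 0.9 and 0.1 for each drug. Interaction η ~ N(0, SD 0.56).
- True DLT rates: Table 10.5: 12.
- Overdose control: P(DLT rate ≥ 0.33) < 0.25 (Section 7.1.2). Escalation limited to 100%, cohorts of 3, start at 100/240 mg.
- Reference doses: 200 mg for BI 891065. For BI 754091, Section 7.1.2 prints 3200 mg; I use d2* = 240 mg as an assumption and vary it.

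**Model.** logit π1 = log α1 + β1 log(d1/200); logit π2 = log α2 + β2 log(d2/d2*); π0 = π1 + π2 − π1π2; odds(π12) = odds(π0) × exp(η × d1/200 × d2/d2*).

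**Reproducing the plan's own figures first (d2* = 240 mg).**
- Prior P(overdose) at 50, 100, 200 and 400 mg: 0.032, 0.051, 0.159, 0.435. Table 10.5: 10 prints 0.033, 0.053, 0.162, 0.435.
- Table 10.5: 11: Scenario 3, 0.257 (printed 0.256); Scenario 5, 0.236 (0.234); Scenario 9, 0.249 (0.249); Scenario 12, 0.109 (0.107).

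With 3200 mg these tables are not reproduced.

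**What the rule alone allows.** Ignoring the model, the longest trial has 12 patients at one dose and then two cohorts at each of the other three: 12 + 3 × 6 = 30. So 30 is not excluded by the rule's wording. It has to be checked against the doses that the model would recommend.

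**Rule plus model.** Each path has a probability given by its binomial cohort outcomes, so patient numbers and selections follow by enumeration, with no simulation error of their own.

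| Scenario | Mean N, recomputed | Mean N, printed | Difference | Max N, recomputed | Max N, printed |
|---|---|---|---|---|---|
| 1 | 12.56 | 12.711 | −1.2% | 18 | 30 |
| 2 | 11.82 | 11.538 | +2.5% | 18 | 30 |
| 3 | 13.15 | 13.752 | −4.4% | 18 | 30 |
| 4 | 12.21 | 12.414 | −1.6% | 18 | 27 |

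The maximum stays at 18 with d2* = 200 or 225 mg, or with a 50 mg start. It is 21 with d2* = 3200 mg.

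**Selection percentages at d2* = 240 mg.** SE = √(p(1−p)/1000), with p the recomputed value.

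| Cell | Recomputed | Printed | SE | Gap in SE |
|---|---|---|---|---|
| Scenario 1 overdose | 6.3% | 9.3% | 0.77 | 3.0/0.77 = 3.9 |
| Scenario 2 overdose | 30.5% | 35.5% | 1.46 | 5.0/1.46 = 3.4 |
| Scenario 3 underdose | 80.5% | 76.2% | 1.25 | 4.3/1.25 = 3.4 |
| Scenario 4 target | 57.7% | 64.9% | 1.56 | 7.2/1.56 = 4.6 |

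**Sensitivity of these cells.** With a reference dose of 225 to 230 mg, the first three are 6.3%, 30.6% and 80.5%; with 200 mg they are 5.0%, 25.9% and 83.6%. Scenario 4 target is less stable: 62.8% at 225 to 230 mg, where the gap is 2.1/1.53 = 1.4 SE, and 61.3% at 200 mg. Small changes move paths between neighbouring doses that are nearly tied.

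**Other rules tried (d2* = 240 mg).**
- Section 7.1.2 rule: means 8.6 to 12.1, maximum 18.
- The 6-patient limb alone: maximum 21.
- Both limbs required together: reaches 30, but means are 12.99 to 15.33 even when trials still running at 30 are left out.
- Closest on selection: stop only when the dose just given is recommended again, has at least 6 patients, and either P(target) is at least 0.5 or the total is at least 12. Under/target/over for Scenarios 1 to 4: 19.2/72.7/7.3, 5.8/52.4/34.4, 77.0/22.9/0, 34.7/64.8/0.1. Printed: 19.4/70.4/9.3, 6.9/51.1/35.5, 76.2/23.1/0, 34.5/64.9/0.2. The documents do not state this rule; it only suggests where the table may have come from.

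**The case against.** The limit of 18 needs the model and an inferred reference dose; the rule by itself permits 30. The sponsor used JAGS, with its own posterior noise, and near-tied recommendations make individual percentages unstable: a cruder posterior approximation moved Scenario 2 overdose from 30.5% to 28.8%. This is fair. It rules out treating the first decimals as exact and weakens the Scenario 4 comparison. It does not rescue the maxima: adding heavy posterior noise raised the largest trial only to 21.

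The practical effect is limited. The appendix uses data as of October 2018, the Safety Review Committee decides on updated posteriors, and Section 7.1.2 gives posteriors from actual Part B data. In Scenarios 1 and 2 the printed overdose rates are higher than the recomputed ones, so the table does not understate that risk there. The SAP (Section 7.4) also points to its own Section 9.1 for the Part B prior. That section is not in the available copy, so another description may exist.

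A reader might infer three stronger things, none of which holds.
- *That the printed means are impossible.* They agree to within about 5%. A Scenario 2 mean below 12 is possible because 6.5% of trials stop early: the floor is 0.935 × 12 + 0.065 × 3 = 11.4, below 11.538.
- *That the planned size contradicts the simulation.* Section 7.7 says "Approximately 31-37 patients (including patients at the MTD) will be expected for this part", but bases this on dose levels and cohorts and says that enrolment cannot be predicted. Replacements, confirmation patients and b.i.d. cohorts were not simulated.
- *That the printed minimum of 1 DLT in Scenario 1 identifies another rule.* A trial with no DLTs has probability 0.853³ × 0.789⁶ × 0.658⁶ = 0.012, so about 12 in 1000 are expected. The same 1.2% arises under the closest-matching rule, so the discrepancy cannot tell the rules apart.

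**Conclusion.** The point holds for the maxima and for part of the selection results. Under the described rule, with the printed prior, no trial exceeds 18 patients (21 with the printed 3200 mg reference dose), against 27 to 30 in the table. Scenario 1 overdose (about 6% against 9.3%) and Scenario 3 underdose (about 80% against 76.2%) differ by more than the error of 1000 trials, and do so for reference doses of 225 to 240 mg. Scenario 2 overdose (about 30% against 35.5%) also differs, with somewhat more sensitivity to the posterior approximation. Scenario 4 target (about 58% against 64.9%) differs at 240 mg but not clearly at 225 to 230 mg. Neither the Appendix 10.5 rule nor the Section 7.1.2 rule yields Table 10.5: 13. The conclusion rests on the Table 10.5: 8 prior having been used as printed and on the 240 mg inference, which the 3200 mg result bounds for the maxima. It is a fault in the documentation of the design's properties. It does not show that any dose decision was wrong.

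**What to change.** State in Appendix 10.5 the stopping rule actually simulated, including any cap on patient numbers, and the BI 754091 reference dose used, and reconcile the latter with Section 7.1.2. Otherwise re-run Table 10.5: 13 under the rule to be used. Then revise the text that rests on the table: that patient numbers are in line with expectation, that Scenario 4 hits the target in just under 65% of trials, and that the model is insensitive to misspecification. The cost is one simulation run and a few sentences; some percentages may become less favourable. Adding the 200 mg b.i.d. level (modelled as 300 mg q.d.) and the planned Part B size to the re-run would be useful but is optional.
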